1.13.2 ACP-319 First-in-Human Study

ACP-319 monotherapy has been evaluated in a first-in-human trial (FIH), dose-escalation study (25 to 400 mg QD) in subjects with relapsed or refractory lymphoid malignancies (Amgen Study #20101262/NCT01300026). Key eligibility criteria included requirements that subjects be ≥18 years old, have an Eastern Cooperative Oncology Group (ECOG) performance status ≤2, and demonstrate adequate organ function. ACP-319 was administered until disease progression or unacceptable toxicity. DLTs were evaluated during the first 28 days of ACP-319 administration.

Enrollment in this study is complete. Because the protocol allowed subjects to continue with ACP-319 treatment until disease progression or intolerable AE, the study is still ongoing. The results from the most recent clinical database review, 31 October 2013, are provided below.

Twenty-eight subjects received ACP-319 (6 at 25 mg; 3 at 50 mg, 100 mg, 200 mg, and 300 mg; and 10 at 400 mg; all doses were given QD). The most common AEs experienced by subjects during the initial assigned dose levels (in at least 25% of subjects) were cough 13 (46%), diarrhea 13 (46%), fatigue 10 (36%), pyrexia 10 (36%), nausea 9 (32%), and anemia 7 (25%). SAEs that occurred in >1 subject each were febrile neutropenia, disease progression, device-related infection, lung infection, and pneumonia (each 2 subjects [7%]), and pyrexia (3 subjects [11%]). SAEs that were assessed by the investigator to be treatment-related (including those occurring after intrasubject dose escalation) occurred in 6 subjects: hemolysis, hypoxia, and pneumonia; hemolysis; pyrexia, *Clostridium difficile* colitis, and infection; abdominal pain and decreased appetite; colitis, neutropenia, and febrile neutropenia; and exfoliative dermatitis.

One subject experienced a DLT (Grade 3 hemolysis). This subject had received rasburicase on the same day as ACP-319; rasburicase is associated with hemolysis and methemoglobinemia and includes a "black box" warning for these events (ELITEK [prescribing information] 2011). One subject died due to a thromboembolic event that was assessed by the investigator as unrelated to ACP-319, and 1 subject died due to disease progression. A trend towards QTcF prolongation was noted in the 400-mg cohort; however, no QTcF >500 msec or increase >60 msec from baseline has been observed.

[figure not shown]
PK data are available from 26 subjects who remained on treatment through Day 29 after receiving daily oral ACP-319 doses of 25 to 400 mg. Median estimates of T_{max} ranged

Protocol: ACE-LY-001

from 0.9 to 2.0 hour and estimates of mean $t_{1/2}$ ranged from 3.0 to 3.9 hour. Mean estimates of C_{max} and AUC_{0-24} were 6.15 µg/mL and 30.2 µg•h/mL, respectively, after 29 days at the 400-mg dose level. ACP-319 plasma exposure generally increased with increasing dose and tended to plateau across the 300- and 400-mg dose levels. Mean ACP-319 accumulation ratios on Day 29 ranged from 0.924 to 1.87.

Consistent reductions in lymphadenopathy were observed at all doses by CT scans (Figure 1-2). Responses were present in all cytogenetic subtypes. At the 200- to 400-mg dose levels, 13 of 15 subjects with CLL remained on study after a median follow-up of 30 weeks (range 14 to 65 weeks). In summary, ACP-319 was well tolerated over periods extending to >18 months and antitumor activity was observed across all dose levels in subjects with CLL.

Figure 1-2. The Maximum Percentage Improvement of the Overall Sum of Cross Product in Nodal and Extra-Nodal Lesions from Radiological Assessment for CLL Subjects Safety Analysis Set

Data collected after the intra-subject dose escalation are not included in this graph.

CR=Complete Remission, CRi=CR with incomplete Marrow Recovery, PR=Partial Remissione, SD=Stable Disease, PD=Progressive Disease, NA=Not Applicable, NE=Non-Evaluable Reporting Period: Inception to 310CT2013

Program: /userdata/earlydev/AMG319/20101262/analysis/primary_analysis/figures/program/f-eff-max-per-impr-overall-nod-radio-cll-eff.sas Output: f14-04-001-002-eff-max-per-impr-overall-nod-radio-cll-eff-l.rtf (Date Generated: 30JAN14 06:58) Source Data: crt.trcrir, crt.subjlvl

1.14 BENEFIT/RISK

Acalabrutinib is a potent, orally administered small molecule inhibitor of BTK. As described in Section 1.13.1, a PK/PD study has been completed with acalabrutinib in healthy volunteers (ACE-HV-001). The safety results showed no safety risk was identified in healthy subjects receiving 1 or 2 days of acalabrutinib ≤100 mg. In the Phase 1/2 study of acalabrutinib in subjects with CLL, an ORR of 95% has been observed with a median follow-up of 14.3 months. In summary, the preliminary data

Protocol: ACE-LY-001

suggest that acalabrutinib is well tolerated and has robust activity as a single agent in the treatment of subjects with CLL including those with 17p del. The nonclinical and toxicology results of acalabrutinib suggest it may have an improved therapeutic window relative to ibrutinib; it may be more readily combined with other agents for the treatment of cancer. For more detailed information on the clinical experience for acalabrutinib please refer to the Investigator Brochure.

ACP-319 has been evaluated in a FIH, dose-escalation study (25 to 400 mg QD) in subjects with relapsed or refractory lymphoid malignancies, as described in Section 1.13.2. The drug was generally well tolerated at all dose levels and no MTD was established over this dose range. In subjects with CLL, the drug showed anticancer activity across all tested doses.

Strong clinical and mechanistic rationale exist to expect increased efficacy with dual inhibition of BTK and PI3K δ (see Section 1.1). Based on known pathway-related side effects as well as nonclinical safety pharmacology (Section 1.6) and toxicology (Section 1.12) studies of the combination of acalabrutinib and ACP-319, improved activity may be achievable without a worsening toxicity profile.

2.0 STUDY OBJECTIVES

2.1 PRIMARY OBJECTIVE

To characterize the safety profile of acalabrutinib and ACP-319 in subjects with relapsed or refractory B-cell malignancies

2.2 SECONDARY OBJECTIVES

To document the extent of study drug exposure as determined by coadministration of acalabrutinib and ACP-319

To evaluate the PD effects of acalabrutinib and ACP-319 administration

To evaluate the activity of acalabrutinib and ACP-319 as measured by response rate, duration of response, progression-free survival, and time-to-next treatment

3.0 STUDY DESIGN

This study is a multicenter, open-label, nonrandomized, sequential group, dose-escalation study to be conducted at approximately 30 sites. The study is divided into 2 parts: Part 1 of the study is the dose-escalation portion and Part 2 allows for possible expansion groups (Figure 3-1).

Protocol: ACE-LY-001

A cycle is defined as a period of 28 days.

Part 1

In each dose-escalation cohort, subjects will take acalabrutinib (and previously ACP-319) BID at approximately 12-hour intervals. The acalabrutinib dose will be fixed at 100 mg BID. The ACP-319 dose will be escalated as follows:

Cohort 1: Acalabrutinib 100 mg BID + ACP-319 25 mg BID continuously

Cohort 2: Acalabrutinib 100 mg BID + ACP-319 50 mg BID continuously

Cohort 3: Acalabrutinib 100 mg BID + ACP-319 100 mg BID continuously

Each dosing cohort will be enrolled sequentially with 6 subjects per cohort. If ≤1 dose-limiting toxicity (DLT) (see below for definition) is observed in the cohort during Cycle 1, escalation to the next cohort will proceed. If ≥2 DLTs are observed during Cycle 1, dosing at that dose and higher will be suspended and the maximum tolerated dose (MTD) will be established as the previous cohort. The MTD is defined as the highest daily dose for which fewer than 33% of the subjects experience a DLT during Cycle 1. Escalation will end with Cohort 3 or sooner if the MTD is reached in an earlier cohort.

Part 1 of the study will include adult subjects with the following disease types:

Non-germinal center B-cell subtype (non-GCB) diffuse large B-cell lymphoma (DLBCL), characterized as de novo

MCL, characterized by documentation of monoclonal B cells that have a chromosome translocation t(11;14)(q13;q32) and/or overexpress cyclin D1 iNHL

- o FL Grade 1, 2 or 3a
- o WM
- o CLL/SLL

Note: Under Amendment 6 of this protocol, all active subjects will receive acalabrutinib monotherapy (100 mg BID).

Part 2

Part 2 consists of expansion groups of up to 12 subjects per histology provided the safety and efficacy results from Part 1 of the study indicate that further evaluation of the combination is warranted. The possible expansion groups for Part 2 could include adult subjects with the following disease types:

Non-GCB DLBCL, characterized as de novo

Protocol: ACE-LY-001

Germinal center B-cell subtype (GCB) DLBCL

Richter's syndrome

MCL, characterized by documentation of monoclonal B cells that have a chromosome translocation t(11;14)(q13;q32) and/or overexpress cyclin D1 iNHL

- FL, Grade 1, 2, or 3a
- o WM
- o CLL/SLL

Multiple myeloma (MM)

B-cell acute lymphoblastic leukemia (B-ALL)

Note: Under Amendment 4 of this protocol, enrollment in Part 2 is closed for all cohorts except the non-GCB DLBCL cohort.

Note: Under Amendment 6 of this protocol, all active subjects will receive acalabrutinib monotherapy (100 mg BID).

Treatment with acalabrutinib (and previously ACP-319), in Part 1 and Part 2, may be continued until disease progression or an unacceptable drug-related toxicity occurs as defined in the protocol. Dose modification provisions are provided in the study protocol. Note: Temporary withholding of study drug for as little as 7 days can cause a transient worsening of disease and/or of constitutional symptoms. Refer to Section 3.12 for more information on assessing disease progression under these circumstances. All subjects who discontinue study treatment will have a safety follow-up (SFU) visit 30 (+ 7) days after the last dose of study drug and will be followed every 3 months thereafter until disease progression or the start of alternative anticancer treatment.

All subjects will have hematology, chemistry, and urinalysis safety panels performed at screening. Once dosing commences (Day 1), all subjects receiving acalabrutinib (and previously ACP-319) combination therapy will be evaluated for safety, including serum chemistry and hematology, on Cycle 1 Days 1, 8, 15, 22, and 28, Cycle 2 Days 15 and 28, then monthly through Cycle 24, and every 3 months thereafter. ECGs will be obtained at screening, repeatedly during Cycle 1, at each study visit through Cycle 6, and at each study visit in Cycles 9 and 12. PK testing will be done in Cycles 1 to 4. PD testing will be done in Cycles 1 and 2, and at the treatment termination (TT) visit. Radiologic tumor assessments will be done at screening and at the end of Cycle 2, Cycle 4, and Cycle 6; every 3 cycles (12 weeks) through Cycle 18, and then every 6 cycles thereafter, or more frequently at the investigator's discretion.

[figure not shown]
Protocol: ACE-LY-001

Refer to Appendix 5 for a comprehensive list of study assessments and their timing (acalabrutinib monotherapy).

Subjects showing clinical benefit and who are tolerating study treatment may remain on study until the end of study, defined as 36 months after the last subject is enrolled. Subjects who are still on treatment at the end of the study and deriving clinical benefit from acalabrutinib monotherapy may be eligible to enroll in a rollover or safety extension study of acalabrutinib monotherapy.

[figure not shown]
Subjects who are still on treatment at the end of the study and deriving clinical benefit from acalabrutinib treatment may continue treatment. At the time of the final data cutoff and database closure, subjects who remain in this study may be transitioned to a separate rollover study or remain within this study for continued access to study drug. Once all active subjects are eligible to continue to receive acalabrutinib and after database closure, this study would be considered closed. There will be no further data collection other than reporting of SAEs per Section 6.3. Access within this study will enable continued treatment with visit assessments per standard of care, whereas the separate rollover study will enable treatment continuation with visit assessments and data collection per the rollover study protocol.

Subjects who meet criteria of progressive disease and are continuing to gain clinical benefit from therapy may be able to temporarily remain on acalabrutinib after discussion with the medical monitor.

Protocol: ACE-LY-001

Figure 3-1. Study Schema

Abbreviations: B-ALL = B-cell acute lymphoblastic leukemia; BID = twice daily; CLL/SLL = chronic lymphocytic leukemia/small lymphocytic lymphoma; DLT = dose-limiting toxicity; FL= follicular lymphoma; GCB = germinal center B-cell diffuse large B-cell lymphoma; MM = multiple myeloma; MTD = maximum tolerated dose; non-GCB DLBCL = non-germinal center B-cell diffuse large B-cell lymphoma; RS = Richter's syndrome; TBD = to be determined; WM = Waldenström macroglobulinemia.

Note: Under Amendment 3 of this protocol, subjects with CLL/SLL in Parts 1 and 2 will receive acalabrutinib monotherapy (100 mg BID).

Note: Under Amendment 4 of this protocol, enrollment in Part 2 is closed for all cohorts except the non-GCB DLBCL cohort.

Note: Under Amendment 5 of this protocol, subjects still deriving clinical benefit from monotherapy may be eligible to enroll in a rollover or safety extension study of acalabrutinib monotherapy.

Note: Under Amendment 6 of this protocol, all active subjects will receive acalabrutinib monotherapy (100 mg BID).

3.1 STUDY PARAMETERS

3.1.1 Safety Parameters

The safety of acalabrutinib and ACP-319 will be characterized by the type, frequency, severity, timing of onset, duration, and relationship to study drug(s) of any treatment-emergent AEs or abnormalities of laboratory tests; SAEs; or AEs leading to discontinuation or dose reduction of study treatment.

For consistency of interpretation, AEs and laboratory results will be coded using the Medical Dictionary for Regulatory Activities (MedDRA), and the severity of AEs will be graded using the Common Terminology Criteria for Adverse Events (CTCAE), Version 4.03 or higher. Standard definitions for seriousness will be applied (see Section 6.2).

Acerta Pharma Confidential Page 48

Protocol: ACE-LY-001

3.1.2 Pharmacokinetic and Pharmacodynamic Parameters

Standard PK parameters for acalabrutinib in plasma will be evaluated in this study. A full description of the PK parameters is provided in Section 5.4.5.

The occupancy of BTK by acalabrutinib will be measured in peripheral blood mononuclear cells (PBMCs) and bone marrow, when available, with the aid of a biotin-tagged acalabrutinib analogue probe. The effect of acalabrutinib and ACP-319 on biologic markers of B-cell function will also be evaluated.

3.1.3 Efficacy Parameters

Standardized response and progression criteria have been established for B-cell malignancies, including WM (Bladé et al. 1998; Durie et al. 2006; Hallek et al. 2008; Owen et al. 2013; and Cheson et al. 2014); assessments of acalabrutinib and ACP-319 efficacy in this study will be based on these criteria. Efficacy endpoints will include:

Overall response rate (ORR)

Duration of response

Progression-free survival

Time-to-next treatment

3.2 RATIONALE FOR STUDY DESIGN AND DOSING REGIMEN

Refer to Protocol Amendment 5.0 for rationale for study design and dosing regimen.

3.3 SELECTION OF STUDY POPULATION

3.3.1 Inclusion Criteria

Eligible subjects will be considered for inclusion in this study if they meet **all** of the following criteria:

Part 1:

- Diagnosis of non-GCB DLBCL, MCL, or iNHL as documented by medical records and with histology based on criteria established by the World Health Organization (WHO).
 - a) If the subject has DLBCL, it is characterized as de novo non-GCB DLBCL (Hans et al. 2004 or Choi et al. 2009). Note: primary mediastinal large B-cell lymphoma (PMBCL) is excluded from this protocol.

Protocol: ACE-LY-001

b) If the subject has MCL, it is characterized by documentation of monoclonal B cells that have a chromosome translocation t(11;14)(q13;q32) and/or overexpress cyclin D1.

- c) If the subject has iNHL, the histology shows 1 of the following subtypes:
 - i) FL Grade 1, 2, or 3a
 - ii) WM
 - iii) CLL/SLL
- 2. Prior treatment for lymphoid malignancy:
 - a) If the subject has DLBCL, there is no curative option with conventional therapy and the prior treatment included ≥1 prior combination chemoimmunotherapy regimen (e.g., anthracycline based therapy with rituximab).
 - b) If the subject has MCL or iNHL, the prior treatment comprised any of the following:
 - i) ≥1 regimen containing an anti-CD20 antibody administered for ≥2 doses and/or
 - ii) ≥1 regimen containing ≥1 cytotoxic agent (e.g., bendamustine, chlorambucil, cyclophosphamide, cytarabine, doxorubicin) administered for ≥2 cycles, and/or
 - iii) ≥1 regimen containing yttrium⁹⁰-ibritumomab tiuxetan (Zevalin®) or iodine¹³¹-tositumomab (Bexxar®).
- Presence of radiographically measurable lymphadenopathy or extranodal lymphoid malignancy (defined as the presence of a ≥2.0 cm lesion as measured in the longest dimension by computed tomography [CT] scan). Note: Not applicable to subjects with WM and MM.
- 4. Absolute neutrophil count (ANC) ≥1.5 x 10⁹/L or platelet count ≥100 x 10⁹/L unless due to disease involvement in the bone marrow.

All Parts:

- 5. Men and women ≥18 years of age.
- 6. Documented active disease.
- 7. Eastern Cooperative Oncology Group (ECOG) performance status of ≤2.

Protocol: ACE-LY-001

8. Females must agree to use highly effective forms of contraception during the study and for 2 days after the last dose of acalabrutinib and 90 days after the last dose of APC-319, whichever is longer, if sexually active and able to bear children. Highly effective forms of contraception are defined in Section 3.11.4.

- 9. Males must agree to use highly effective forms of contraception while taking ACP-319 and for 90 days after their last dose of ACP-319, if sexually active and able to beget children. Males must also refrain from sperm donation during the study and for 90 days after the last dose of ACP-319.
- 10. Willing and able to participate in all required evaluations and procedures in this study protocol including swallowing capsules without difficulty.
- 11. Ability to understand the purpose and risks of the study and provide signed and dated informed consent and authorization to use protected health information (in accordance with national and local patient privacy regulations).

Part 2 Additional disease entry criteria:

- 12. DLBCL (GCB): Confirmed diagnosis of DLBCL with disease characterized as GCB subtype by immunohistochemistry (Hans et al. 2004 or Choi et al. 2009) and meeting the rest of the criteria as defined above, including characterization as de novo DLBCL.
- 13. Richter's syndrome: Confirmed diagnosis of previously treated CLL/SLL with previously untreated and biopsy-proven DLBCL due to Richter transformation and meeting the rest of the criteria as defined above.
- 14. MM: Confirmed diagnosis of MM, which has relapsed after, or been refractory to ≥1 prior therapy for MM and is progressing at the time of study entry and meeting the rest of the criteria as defined above.
- 15. B-ALL: Confirmed diagnosis of previously treated B-ALL and meeting the rest of the criteria as defined above.

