- 10. Use of a strong inhibitor or inducer of cytochrome P450 (CYP)3A (see Appendix 3) within 7 days before dose of study drug or expected requirement for use of a CYP3A inhibitor or inducer during the first 28 days of administration of study drugs.
- 11. Remains not applicable for this amendment.
- 12. Known history of HIV, serologic status reflecting active hepatitis B or C infection, or any uncontrolled active systemic infection.

Protocol: ACE-LY-001

 a) Subjects who are hepatitis B core antibody (anti-HBc) positive and who are surface antigen negative will need to have a negative polymerase chain reaction (PCR) result before enrollment. Those who are hepatitis B surface antigen (HbsAg) positive or hepatitis B PCR positive will be excluded.

- b) Subjects who are hepatitis C antibody positive will need to have a negative PCR result before enrollment. Those who are hepatitis C PCR positive will be excluded.
- 13. Major surgery within 4 weeks before first dose of study drugs. Note: If a subject had major surgery, they must have recovered adequately from any toxicity and/or complications from the intervention before the first dose of study drug.
- 14. History of stroke or intracranial hemorrhage within 6 months before the first dose of study drugs.
- 15. Ongoing, drug-induced liver injury, alcoholic liver disease, nonalcoholic steatohepatitis, primary biliary cirrhosis, ongoing extrahepatic obstruction caused by cholelithiasis, cirrhosis of the liver, or portal hypertension.
- 16. History of or ongoing drug-induced pneumonitis.
- 17. Part 2 only: ANC <0.5 x 10⁹/L or platelet count <50 x 10⁹/L unless due to disease involvement in the bone marrow.
- 18. Estimated creatinine clearance of <30 mL/min, calculated using the formula of Cockcroft and Gault [(140-Age) Mass (kg)/(72 creatinine mg/dL); multiply by 0.85 if female].
- 19. Significant screening ECG abnormalities including left bundle-branch block, second-degree AV block type II, third-degree AV block, Grade ≥2 bradycardia, and QTc >480 msec.
- 20. Breastfeeding or pregnant.
- 21. Concurrent participation in another therapeutic clinical trial.
- 22. History of bleeding diathesis (e.g., hemophilia or von Willebrand disease).
- 23. Requires or receiving anticoagulation with warfarin or equivalent vitamin K antagonists (e.g., phenprocoumon) within 7 days of first dose of study drug.

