3.7 ASSESSMENT OF DOSE-LIMITING TOXICITY

In Part 1, a DLT will be defined as the occurrence of any of the following ACP-319-related AEs:

- 1. Any Grade ≥3 nonhematologic toxicity (except Grade 3 nausea, vomiting, or diarrhea that respond to supportive therapy)
- 2. Any of the following hematologic toxicities (for CLL):
 - a. Grade 4 neutropenia lasting >7 days
 - b. Grade 4 thrombocytopenia, or Grade 3 thrombocytopenia with bleeding, or any requirement for platelets transfusion
 - c. Grade 3 febrile neutropenia (temperature ≥38.5°C)
 - d. Grade 4 anemia, unexplained by underlying disease
- 3. Dosing delay due to toxicity for >28 consecutive days

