| Grade ≤2 | Maintain current dose level and schedule. | Maintain current dose level and schedule. | | | |
| Grade 3 | Maintain current dose level and schedule. | Maintain current dose level and schedule. Monitor ANC at least 1x per week. | | | |
| Grade 4 | Maintain current dose level and schedule and monitor ANC at least 1x per week. If Grade 4 neutropenia lasts for >7 days (neutrophil growth factors are permitted per ASCO guidelines [Smith et al. 2015b] and use must be recorded on the CRF), modify dose as instructed in Table 3-1. | Withhold ACP-319. Monitor ANC at least 1x per week until ANC ≥0.5 x 10 ⁹ /L, then resume ACP-319 at lower dose level (if applicable). | | | |
| | Thrombocytopenia | 1 | | | |
| Grade ≤2 | Maintain current dose level and schedule. | Maintain current dose level and schedule. | | | |
| Grade 3 | If no significant bleeding, maintain current dose level and schedule. In the presence of significant bleeding, modify dose as instructed in Table 3-1. | Maintain current dose level and schedule. Monitor PLT at least 1x per week. | | | |
| Grade 4 | Modify dose as instructed in Table 3-1. | Withhold ACP-319. Monitor PLT at least 1x per week until PLT ≥25 x 10 ⁹ /L, then resume ACP-319 at lower dose level (if applicable). | | | |
| | Rash | T | | | |
| Grade 1 | Maintain current dose level and schedule. | Maintain current dose level and schedule. | | | |
| Grade 2 | Maintain current dose level and schedule. | Withhold ACP-319 until Grade ≤1, consider systemic corticosteroids. May resume ACP-319 at initial or lower dose (if applicable) at investigator discretion. | | | |

Protocol: ACE-LY-001

Table 3-2. Recommendations for Acalabrutinib and ACP-319 Dose Modifications Based on Type and Severity of Treatment-Related Adverse Events or Laboratory Abnormalities

| | Recommendation | | |
|-------------------------------------|-----------------------------------|---------------------------------|--|
| NCI CTCAE Grade | Acalabrutinib | ACP-319 | |
| | Withhold acalabrutinib until | Discontinue ACP-319 | |
| | Grade ≤1, consider systemic | permanently. | |
| Grade = 3 or 4 | corticosteroids. May resume | | |
| 014de - 3 01 4 | acalabrutinib at initial or lower | | |
| | dose level (if applicable) at | | |
| | investigator discretion. | | |
| QTC Interval Prolongation | | | |
| | | Refer to Section 4.1.9. | |
| Other Nonhematologic Adverse Events | | | |
| Grade ≤2 | Maintain current dose level | Maintain current dose level and | |

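### Part 1 inclusion criterion 4 joins neutrophils and platelets with *or*, so one adequate count qualifies a subject without marrow involvement and the other count has no numeric floor

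*Protocol*

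**What the plan says.** Section 3.3.1 opens with the rule that "Eligible subjects will be considered for inclusion in this study if they meet all of the following criteria". Criterion 4, listed under Part 1, is a single criterion with two limbs: "Absolute neutrophil count (ANC) ≥1.5 x 10⁹/L or platelet count ≥100 x 10⁹/L unless due to disease involvement in the bone marrow". The synopsis carries the same wording.

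The only other numeric limit on these counts is exclusion 17 in Section 3.3.2: "Part 2 only: ANC <0.5 x 10⁹/L or platelet count <50 x 10⁹/L unless due to disease involvement in the bone marrow".

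Table 3-2 (Section 3.9) gives the ACP-319 advice for Grade 4 events. For neutropenia it is "Withhold ACP-319. Monitor ANC at least 1x per week until ANC ≥0.5 x 10 ⁹ /L". For thrombocytopenia it is "Withhold ACP-319. Monitor PLT at least 1x per week until PLT" is at least 25 x 10⁹/L. For acalabrutinib, Grade 4 thrombocytopenia refers to Table 3-1, where the action is to hold. Grade 4 neutropenia reads "Maintain current dose level and schedule and monitor ANC at least 1x per week. If Grade 4 neutropenia lasts for >7 days", and only then does Table 3-1 apply.

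Section 3.7 includes among the hematologic DLTs "Grade 4 thrombocytopenia, or Grade 3 thrombocytopenia with bleeding, or any requirement for platelets transfusion". It heads that list as being for CLL and confines DLTs to events related to ACP-319.

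**The concern.** *Or* is the right connective in an exclusion, where either low count should bar entry. In an inclusion criterion it does the opposite, because either adequate count lets the subject in. The limits of 1.5 and 100 look like a stricter Part 1 standard that exclusion 17 relaxes to 0.5 and 50 for Part 2. That ordering holds only if Part 1 requires both counts. As written, the part that sets the dose has no lower limit on the second count, while the part that follows it does.

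What is at stake is mainly the reading of Part 1. A subject who starts with one severely low count makes later cytopenia hard to assign to ACP-319 or to the subject's prior state. Section 3.11.1 also reports serious and fatal hemorrhage and Grade 3 or 4 cytopenias with acalabrutinib, so the missing floor has a safety side as well.

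**Working it through.** The plan gives no figure to reproduce here. The check is one of logic.

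**Inputs** (all counts x 10⁹/L)
- Criterion 4 as written: ANC ≥1.5 *or* platelets ≥100, waived for marrow involvement (Section 3.3.1, synopsis).
- The same criterion with *and*.
- Exclusion 17: ANC <0.5 or platelets <50, waived for marrow involvement, Part 2 only (Section 3.3.2).
- Stand-in for Grade 4: ANC <0.5 or platelets <25. The protocol does not print the hematologic grade limits, so these are taken from the resume limits in Table 3-2.

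**Grid.** ANC 0.3, 0.49, 0.5, 1.0, 1.49, 1.5, 3.0 (7 values) and platelets 15, 24, 25, 49, 50, 99, 100, 200 (8 values).
- Pairs with ANC <0.5: 2 x 8 = 16.
- Other pairs with platelets <25: 5 x 2 = 10.
- Grade 4 pairs in all: 16 + 10 = 26.

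**Without marrow involvement**
- *Or* admits low ANC with platelets ≥100 (2 x 2 = 4) and low platelets with ANC ≥1.5 (2 x 2 = 4): 8 of 26.
- *And* admits 0 of 26.
- Exclusion 17, if it applied, would let in 0 of 26.

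| Subject, no marrow involvement | Criterion 4 as written | With *and* | Exclusion 17 (Part 2 only) | Table 3-2 for ACP-319, if treatment-related |
|---|---|---|---|---|
| ANC 0.3, platelets 200 | qualifies | fails | excluded | withhold |
| ANC 3.0, platelets 15 | qualifies | fails | excluded | withhold |

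**With marrow involvement.** All 26 pairs pass under *or*, under *and* and under exclusion 17, because each carries the waiver.

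The 8 of 26 counts grid points. It is not an estimate of how many subjects are affected.

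**Weight of one attribution.** Each cohort has 6 subjects. Escalation proceeds at 1 DLT or fewer and stops at 2 or more (Section 3.5). One subject is 1/6 = 16.7%. Moving from 1/6 (16.7%) to 2/6 (33.3%) crosses the requirement that fewer than 33% have a DLT. So if a cohort has one other DLT, a single disputed cytopenia decides it.

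**The case against.** Several parts of the opposing case stand.

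- **Table 3-2 does not flatly contradict criterion 4.** A reader might infer that a subject can be eligible on Day 1 at a count where the protocol requires drug to be withheld. The documents do not support that. The table's title limits it to treatment-related events or abnormalities, and Section 3.9 calls its content guidelines from which investigators may depart. A count that was low before the first dose is not treatment-related. The advice also differs by drug, since acalabrutinib is continued in Grade 4 neutropenia unless it lasts more than 7 days.
- **A low baseline count is not itself a DLT.** Section 6.2.1 does not treat an unchanged pre-existing condition as an adverse event, so it cannot be an ACP-319-related one.
- **The DLT route is narrow.** The hematologic list is for CLL, and from Amendment 3 CLL/SLL subjects receive acalabrutinib monotherapy.
- **Entry is reviewed.** The medical monitor confirms eligibility (Section 3.3.4), and exclusion 2 gives the investigator discretion. Neither sets a count.
- **Timing.** At Amendment 6 all active subjects are on monotherapy and the Part 2 regimen is already stated, so a changed criterion would not alter any past escalation decision.

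These points limit the consequence. They do not change what criterion 4 says: no numeric criterion stops a Part 1 subject with one very low count and no marrow involvement.

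**Conclusion.** The point holds as a moderate one. Criterion 4, in both places, is met by one adequate count, and the only rule that would catch the other count is confined to Part 2. For a single very low count the escalation part is therefore looser than the expansion part.

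The consequence is blurred attribution when a subject enters near the levels at which Table 3-2 advises withholding ACP-319. A later worsening then has to be assigned by judgment, mainly for the CLL hematologic DLTs.

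The conclusion rests on reading *or* literally and on subjects without marrow involvement. The documents do not show that any such subject enrolled, had doses held or was misclassified. It would go too far to say that the Part 1 DLT counts are wrong, or that the protocol lacks any baseline safeguard in its DLT definition.

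**What to change.** In criterion 4, in the synopsis and in Section 3.3.1, replace *or* with *and* so that it is clear both counts must be met, and keep the marrow-involvement exception. In the same edit, reconcile it with exclusion 17 and Table 3-2. Say which part each count rule governs, because the Part 2 disease criteria (12 to 15) refer back to the criteria above them. No new threshold is proposed, and no new DLT rule is needed given Section 6.2.1.

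In reporting, list baseline ANC and platelets, with marrow status, for each Part 1 subject beside the DLT results. At this stage that is the more useful half of the change, since it lets a reader see whether the gap was ever used.

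The cost is one word in two places, a clarifying clause and one listing. The downside is small: a few candidates with one low count unrelated to marrow disease would not qualify. The change does nothing for subjects with marrow involvement, whose low counts are admitted under either connective.
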